9.1 Adverse Response Definitions

Adverse Event (AE): An AE refers to any untoward medical occurrence (sign, symptom or disease) in a trial subject that does not necessarily have a causal relationship with the study device. AEs may be classified as 'unanticipated adverse device effects,' 'serious AEs,' 'significant AEs,' or 'non-significant AEs,' as defined below.

Classification	Definition
Serious Adverse Event	Those events that are life-threatening, or result in permanent impairment of a body function, or permanent damage to a body structure or necessitate medical (therapeutic) or surgical intervention to preclude permanent impairment of a body function or permanent damage to a body structure.

Unanticipated Adverse Device Effect	Adverse events in a clinical trial that were not previously identified in the protocol in terms of nature, severity, or degree of incidence. An Unanticipated Serious Adverse Device Effect is an unanticipated adverse event that is serious in nature and caused by or associated with the device and is considered reportable.
Significant Adverse Event	Those non-serious adverse events that occur with contact lens usage that are not sight-threatening but are usually symptomatic and may warrant therapeutic management and /or temporary or permanent discontinuation of contact lens wear.
Non-Significant Adverse Events	Those less severe non-serious adverse events that occur with contact lens usage that are not sight-threatening, may or may not be symptomatic and may warrant palliative management, such as ocular lubricants or temporary interruption of contact lens wear.

AE classification, coding (for reporting to the sponsor) and examples are provided in the following table of Contact Lens Adverse Event Classification and Reporting:

Code	Condition	Potential AE Classification	Reporting
01	Presumed infectious corneal ulcer	SERIOUS	Notify sponsor as soon as possible, within 24 hrs ; IRB reporting as per requirements
02	Permanent loss of ≥ 2 lines of best spectacle corrected visual acuity (BSCVA)	SERIOUS	
03	Corneal injury that results in permanent opacification within central cornea (6mm)	SERIOUS	
04	Neovascularization within the central 6mm of cornea	SERIOUS	
05	Uveitis or Iritis	SERIOUS	
06	Endophthalmitis	SERIOUS	
07	Hyphema	SERIOUS	
08	Hypopyon	SERIOUS	
09	Persistent epithelial defect	SERIOUS	
00	Other serious event	SERIOUS	
11	Peripheral non-infectious ulcer (outside central 6mm)	SIGNIFICANT	Notify sponsor as soon as possible, within 5 working days; IRB reporting as per requirements
12	Symptomatic corneal infiltrative events	SIGNIFICANT	
13	Superior epithelial arcuate lesions (SEALs) involving epithelial split	SIGNIFICANT	
14	Any temporary loss of ≥ 2 lines BSCVA for ≥ 2 wks	SIGNIFICANT	
15	Corneal staining \geq dense coalescent staining up to 2mm in diameter (i.e. moderate staining)	SIGNIFICANT	

16	Corneal neovascularization \geq 1.0mm to 1.5mm vessel penetration (if 2 Grade change from baseline)	SIGNIFICANT
17	Any sign and/or symptom for which subject is administered therapeutic treatment or which necessitates discontinuation of lens wear for \geq 2 weeks	SIGNIFICANT
10	Other significant event	SIGNIFICANT
21	Conjunctivitis: bacterial, viral, allergic	NON-SIGNIFICANT
22	Papillary conjunctivitis if \geq mild scattered papillae/follicles approximately 1mm in diameter (if 2 Grade change from baseline)	NON-SIGNIFICANT
25	Asymptomatic corneal infiltrative events	NON-SIGNIFICANT
26	Localized allergic reaction	NON-SIGNIFICANT
27	Contact dermatitis	NON-SIGNIFICANT
28	Any sign and/or symptom for which temporary lens discontinuation for $>$ 1 day is recommended	NON-SIGNIFICANT
20	Other non-significant sign and/or symptom	NON-SIGNIFICANT

Normal or adaptive symptoms

Transient symptoms such as end-of-day dryness, lens awareness, itching or burning or other discomfort may occur with contact lens wear and may occasionally reduce wearing time. **These are not reported as adverse events unless they are unexpected in nature, severity or rate of occurrence.**

9.2 Procedures for Adverse Events

Treatment of an adverse event will depend on its nature and severity. Based on the clinical judgment of the investigator the subject may be referred to an ophthalmologist for treatment. The investigator will attempt to determine whether the reaction is related to the test device or a result of other factors.

An Adverse Event Form will be completed for each adverse event. If both eyes are involved, a separate Adverse Event Form will be completed for each eye. Whenever possible, the adverse event will be photo-documented.

Expenses incurred for medical treatment as part of study participation will be paid by the sponsor (bills and prescription receipts kept). The subject must be followed until resolution and a written report completed indicating the subsequent treatment and resolution of the condition.

[figure not shown]
9.3 Reporting Adverse Events

All potential **Serious and Unanticipated Adverse Device Effects** that are related or possibly related to subject participation in the investigation will be reported to the Principal Investigator and the sponsor within 24 hours of the investigator becoming aware of the event. The Principal Investigator will report the event to the EC/IRB as soon as possible (by fax, mail/delivery, phone, or email), but within 10 business days of becoming aware of the problem. *All fatal or life threatening events will be reported immediately to the IRB.*

Significant and Non-Significant Adverse Events will be reported to the sponsor as soon as possible, but no later than 5 working days after the occurrence.

Sponsor contact details are:

Contact:

9.4 Discontinuation from the Study

All discontinuations will be fully documented on the appropriate CRF Exit and Adverse Event forms as needed. Participants will be followed until resolution (in most instances) and are free of the ophthalmic insert related complications or other ocular pathology. When possible study lenses involved in an Adverse Event will be returned to the sponsor in a new tightly sealed contact lens case, and labeled with the subject identification and stored in Unisol non-preserved saline.

10 Statistical Analysis

10.1 Statistical analysis

Summary statistics will be produced, (e.g. mean, standard deviation), by the principal investigator ([name]). Differences between lenses will be compared using Paired t-tests. Paired t-tests /analysis of variance for normal (interval/continuous) data, Wilcoxon's signed ranks test for non-normal (ordinal) data, chi-squares test for nominal data. A Chi-Square test will be used to evaluate lens preference questions.

A sample size of 33 subjects was calculated which provides 80% power to detect a difference of half a line in logMAR high contrast visual acuity (HCVA). The critical alpha level for statistical significance will be set at $p \leq 0.05$, with adjustment for multiple comparisons. All participants who are evaluated in the study will be used in the analysis. In the event of missing data, individual numbers points will be excluded in the analysis and not extrapolated from the collected data.

11 Data Quality Assurance

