Center Destination (Mexico)	School of Optometry Clinic, National Autonomous University (UNAM)
Number of Centers	Single Center
Patient Follow-up	
Subjects enrolled in this study will be followed up after the lens dispensing session:
 
 • Post dispensing follow-up at 1 hour for each study lens pair
Primary Endpoint	High contrast visual acuity
Secondary Endpoints	Lens fitting characteristics, subjective ratings, preference, and ocular response.

Table of Contents

1	Introduction	6
2	Study Objective	6
3	Study Hypothesis	6
3.1	Study Hypothesis	6
4	Study Design	6
5	Investigational Sites	6
5.1	Number of Sites	6
5.2	Investigator Recruitment	7
6	Ethics Review / Statement of Compliance	7
6.1	Relevant Standards / Guidelines	7
6.2	Institutional Review Board	7
6.3	Clinical Trial Registration	7
6.4	Informed Consent	7
7	Potential Risks and Benefits to Human Subjects	8
8	Materials and Methods	8
8.1	Participants	8
	Inclusion criteria	8
8.2	Study Materials	9
8.2.1	Contact lens	9
8.2.2	Contact Lens care	10
8.2.3	Storage of Study Medications/Treatments	10
8.2.4	Clinical Supply Inventory	10
8.2.5	Disposal of Consumables	10
8.2.6	Masking and Control of Study Materials	10
8.2.7	Ordering and Accountability of Study Materials	10
8.3	Visit Schedule and Procedures	11
8.3.1	Visit 1 after dispensing (Fit lenses / Evaluate [e.g. P1])	11
8.3.2	Visit 2 after 1 hour (Assess lenses / Study exit)	12
9	Adverse Event Reporting	12
9.1	Adverse Response Definitions	12
9.2	Procedures for Adverse Events	14
9.3	Reporting Adverse Events	15
9.4	Discontinuation from the Study	15
10	Statistical Analysis	15
10.1	Statistical analysis	15

11 Data Quality Assurance	16
11.1 Study monitoring.....	16
11.2 Record keeping	16
11.3 Record retention	16
11.4 Data Entry / Data Management	16
11.5 Confidentiality.....	16
11.6 Publication.....	16
12 Study Costs and Subject Compensation.....	17
13 Appendixes.....	18

1 Introduction

Biomedics XC is part of an older generation of a hydrogel contact lens portfolio from CooperVision which will be discontinued soon.

Therefore, CooperVision is interested in switching wearers of the Biomedics XC brand into the Proclear hydrogel or Clariti® elite silicone hydrogel contact lenses. A non-dispensing fitting study is proposed to evaluate the clinical performance of these lenses.

2 Study Objective

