8.3 Visit Schedule and Procedures

This will be a randomized, double masked, bilateral, non-dispensing fitting study. Participants will be examined at two different points over the course of one day, V1 (lens dispensing), V2 (1 hour post lens settling). They will wear three different pairs of lenses in randomized fashion. Anterior ocular health examination will be performed at baseline without the use of fluorescein*.

Next, the study lenses will be dispensed and fit evaluated. After 1 hour of wear, lens fit assessments will be collected and the lenses removed. Anterior ocular health examination will be performed with fluorescein and the subjects exited from the study. This same procedure will be repeated at a different day for each lens pair.

** Fluorescein will not be used before lens dispensing to prevent potential eye discomfort that could influence subjective comfort ratings after lens fitting and settling. However, fluorescein will be instilled at the 1 hour visit upon lens removal.*

The following outline identifies the two study visits and the general procedures, (Appendix 5), to be conducted at each visit for each day of the study and recorded in the case report forms (Appendix 6):

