8.3.1 Visit 1 after dispensing (Fit lenses / Evaluate [e.g. P1])

- Explanation of the study
- Sign informed consent form
- Anterior ocular health examination (Slit lamp without fluorescein)
- Insert lenses from pair # 1
- Visual acuity
 - High contrast, monocular logMAR
 - High contrast, binocular log MAR
- Subjective assessments
 - Handling on insertion (0 -100 scale). **Subject to insert study lenses and rate handling.**
 - Comfort on insertion (0 -100 scale)
 - Burning/stinging (0 – 100 scale)
 - Comfort preference (right vs. left)
- Lens fit assessment
 - Lens centration (optimum, decentration acceptable, decentration unacceptable)
 - Corneal coverage [Y/N]
 - Post blink movement (0-5 Likert scale)
 - Lens tightness on push-up test (0% - 100% in 5% steps)
 - Overall fit acceptance (0 – 4) and reason if Grade 2 or less.
 - Investigator's fit preference

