8.3.2 Visit 2 after 1 hour (Assess lenses / Study exit)

- Subjective assessments
 - Comfort on insertion (0 -100 scale)
 - Comfort preference (right vs. left)
 - Handling on removal (0 -100 scale)
- Lens fit assessment
 - Lens centration (optimum, decentration acceptable, decentration unacceptable)
 - Corneal coverage [Y/N]
 - Post blink movement (0-5 Likert scale)
 - Lens tightness on push-up test (0% - 100% in 5% steps)
 - Overall fit acceptance (0 – 4) and reason if Grade 2 or less.
 - Investigator's fit preference
 - Lens removal by subject
- Anterior ocular health examination with fluorescein
- Study exit form must be completed
- Subjects will be required to come to the clinic on a separate day to be fitted with the other study lenses.
- The same procedure as section 8.3.1 and 8.3.2 will be performed for the rest of the lens pairs.

9 Adverse Event Reporting

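### Ocular response: the between-lens tests in 10.1 make no use of the same-day pre-lens examination, which costs some precision but causes no bias

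*Combined protocol and SAP*

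**What the plan says.** The Protocol Synopsis lists the secondary endpoints as "Lens fitting characteristics, subjective ratings, preference, and ocular response".

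Section 8.3 sets two eye examinations on a lens day. Before the lenses go in: "Anterior ocular health examination will be performed at baseline without the use of fluorescein". After 1 hour of wear and removal: "Anterior ocular health examination will be performed with fluorescein and the subjects exited from the study". The cycle is then repeated: "This same procedure will be repeated at a different day for each lens pair". Sections 8.3.1 and 8.3.2 list the same two examinations, and 8.3.2 applies both lists to the remaining pairs.

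The difference in fluorescein use is deliberate. The footnote to 8.3 explains: "Fluorescein will not be used before lens dispensing to prevent potential eye discomfort that could influence subjective comfort ratings".

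Section 10.1 is the only analysis text. It opens the comparison with "Differences between lenses will be compared using Paired t-tests" and then assigns tests by type of data: paired t-test or analysis of variance for continuous data, Wilcoxon signed ranks for ordinal data, chi-square for nominal data and preferences. It does not name ocular response, and it mentions no baseline, change, shift or covariate.

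**The concern.** A response to a lens is a departure from the state of the eye before that lens went in. The three pairs are worn on three different days, and an eye may be a little redder on one day than on another for reasons unrelated to the lens. If the tests take only the 1-hour finding, that variation stays in each between-lens difference as noise. The schedule already provides a same-day pre-lens examination that could remove part of it, but 10.1 does not use it.

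At stake is the precision of the lens comparison on one secondary endpoint, for signs visible without fluorescein. Because 10.1 is silent, the choice between 1-hour values, changes and adjusted values also remains open until the data are in hand.

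**Working it through.** **1. What can be adjusted.** Each pair has its own pre-lens and 1-hour examination on the same day (8.3, 8.3.1, 8.3.2). Signs seen in white light, such as hyperaemia, can be recorded at both. Corneal staining needs fluorescein, which is used only after removal, so it has no like-for-like pre-lens value.

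**2. Whether the signs are graded.** The visit sections speak of an examination and state no scale. Section 8.1 excludes grade 2-4 anterior segment abnormalities, and adverse event codes 16 and 22 in 9.1 require a 2-grade change from baseline. Grading against a baseline is therefore implied, but the procedures and case report forms (Appendices 5 and 6) are not in the text available here.

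**3. The plan's own figure.** There is none for ocular response. The 33 subjects in 10.1 relate to high contrast visual acuity only, so there is nothing to reproduce on this point.

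**4. Effect on variance.** For two lenses in one subject, let D be the difference in 1-hour grade and B the difference in pre-lens grade, with r = corr(D, B). Relative to using D alone:

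- covariate adjustment: 1 - r²
- plain change score (equal variances assumed): 2(1 - r)

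| r (assumed) | 1 - r² | 40/(1 - r²) | 2(1 - r) |
|---|---|---|---|
| 0.1 | 0.99 | 40.4 | 1.80 |
| 0.3 | 0.91 | 44.0 | 1.40 |
| 0.5 | 0.75 | 53.3 | 1.00 |
| 0.7 | 0.51 | 78.4 | 0.60 |

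The third column is the number of unadjusted subjects that 40 adjusted subjects would match. A change score loses precision when r is below 0.5. A covariate costs about one degree of freedom.

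**5. The same in terms of power.** Assume a standardised difference of 0.45 (not in the documents), n = 40 and two-sided 0.05 without multiplicity adjustment. The noncentral-t power, with noncentrality 0.45 × √40 / √(1 - r²), is 79.3% unadjusted. It becomes 79.7% at r = 0.1, 80.9% at r = 0.2, 82.9% at r = 0.3, 89.3% at r = 0.5 and 97.3% at r = 0.7. Section 10.1 calls for a multiplicity adjustment without naming one. Under an assumed Bonferroni split over three pairs (0.05/3), the unadjusted power is 64%.

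**6. Bias and type I error.** A null simulation of 20,000 trials with n = 40 assumed a day SD of 0.5 and a residual SD of 0.3 grade units. The 1-hour-only and change-score analyses each had a mean estimate of about 0 and a type I error of 5.1%. Their standard errors were 0.131 and 0.096. The algebra agrees:

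- 1-hour only: √[2(0.25 + 0.09)/40] = 0.130
- change score: √[4(0.09)/40] = 0.095

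These SDs imply r = 0.25/0.34 = 0.74, which favours adjustment.

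**The case against.** A reader might infer that day-to-day differences in the eye will be counted as lens effects, so that false differences between lenses are to be expected. The documents do not support this. Order is randomised within subject, so such differences balance across lenses on average. Any chance imbalance in one trial is ordinary sampling error, which the alpha level already covers.

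A reader might also infer that 10.1 commits to an analysis of 1-hour values alone. It does not. A paired t-test or a Wilcoxon test could be run on same-day changes, and ordinal grades would fall under the Wilcoxon provision rather than the paired t-test sentence. The defect is an omission, not a stated wrong method.

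Three further objections have weight:

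- The gain may be small. Section 8.1 requires clear corneas and excludes grade 2-4 abnormalities, which narrows the pre-lens range at entry and may keep r low. At r = 0.1 the benefit is negligible.
- The variance formulas are normal-theory, whereas slit-lamp grades are likely to be coarse and heavily tied. An ordinal model on mostly 0-1 grades in 40 subjects may be unstable.
- Ocular response is absent from the key variables (section 2), the hypotheses (3.1) and the sample-size basis (10.1).

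These points limit the size and priority of the matter. They do not remove it: the examination is already scheduled on every lens day, and the analysis text gives it no role.

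**Conclusion.** The point holds as a low-priority gain in precision. The variance saving ranges from about 1% at r = 0.1 through 25% at r = 0.5 to 49% at r = 0.7. These values are illustrative, and the saving is probably smaller for coarse grades.

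The conclusion rests on three assumptions: r is not given and is shown as a range; at least some white-light signs are recorded on the same scale at both examinations; and randomisation of order is carried out as described. Staining lies outside the point, because its missing pre-lens value is a reasoned choice to protect the comfort ratings.

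**What to change.** Add to 10.1:

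- Name the white-light slit-lamp signs that make up ocular response and the scale used at both examinations.
- For each such sign, compare lenses on the 1-hour grade with the same-day pre-lens grade as a covariate in a within-subject model.
- Tabulate shifts from the same-day pre-lens grade by lens. If grades are too sparse for the model, report the shift table only.
- State that staining and other fluorescein-only signs are post-lens only and unadjusted.

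The cost is a few sentences and a little more analysis, with no added visits or subjects. No new data are needed provided the case report form already records these signs on one scale at both examinations. This should be confirmed before the text is fixed.

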3.1 Study Hypothesis

- Null hypothesis (H₀): There is no difference in high contrast visual acuity, lens fitting characteristics, and subjective assessments between lens types.
- Alternative hypothesis (H₁): There is a difference in high contrast visual acuity, lens fitting characteristics and subjective assessments between lens types.

4 Study Design

This is a 40-subject, double masked, randomized, bilateral, non-dispensing fitting trial comparing hydrogel and silicone hydrogel lens materials. It is anticipated that this study will involve 2 visits for each lens pair, as follows: Visits: V1 (lens dispensing), V2 (1 hour post lens settling). Each subject will be randomized to wear each pair bilaterally in a series of three short fitting comparisons.

5 Investigational Sites

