8.2 Study Materials

8.2.1 Contact lens

All subjects will be trial fitted and, if suitable, dispensed the first pair of lens brand assigned per a predetermined randomization table (Appendix 3). The lenses used in this study are all FDA approved

Confidential

9

and marketed products. Details of the study contact lenses are shown in Table1 and will be provided by the Sponsor.

Table1: Study lens parameters

Brand	Biomedics XC	Clariti Elite Aspheric	Proclear Monthly
Manufacturer	CooperVision	CooperVision	CooperVision
Material	Omafilcon A	Somofilcon A	Omafilcon A
WC %	60%	56%	62%
Base Curve	8.5	8.6	8.6
Lens Diameter	14.2	14.2	14.2
Lens Powers	-1.00 to - 6.00 (in 0.25 steps)	-1.00 to - 6.00 (in 0.25 steps)	-1.00 to - 6.00 (in 0.25 steps)
Replacement schedule	Daily	Daily	Daily

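### The lens comparisons in Section 10.1 omit the day of wear; adjusting for period would protect precision at almost no cost

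*Combined protocol and SAP*

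**What the plan says.** Section 4 sets out the within-subject design: "Each subject will be randomized to wear each pair bilaterally in a series of three short fitting comparisons". Section 8.3 adds that "They will wear three different pairs of lenses in randomized fashion" and, on timing, that "This same procedure will be repeated at a different day for each lens pair". Section 8.2.1 says that the first pair is "assigned per a predetermined randomization table (Appendix 3"); that appendix is not in the supplied text. The protocol does not use the word crossover, but three lenses, three days and a randomised order make it one.

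For the analysis, Section 10.1 says "Differences between lenses will be compared using Paired t-tests" and then, by data type, "Paired t-tests /analysis of variance for normal (interval/continuous) data", with signed-rank tests for ordinal data and chi-square tests for nominal data. No factors are listed for the analysis of variance. No period, day or sequence term appears anywhere in the supplied text. The same section gives the sample size ("A sample size of 33 subjects was calculated which provides 80% power to detect a difference of half a line in logMAR") and says of missing data that "individual numbers points will be excluded in the analysis and not extrapolated from the collected data".

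**The concern.** A paired t-test treats the difference between two lenses in one subject as the lens effect plus noise. Here the two lenses are worn on different days, and which comes first varies between subjects. If scores drift from day to day, the drift adds to the difference in some subjects and subtracts from it in others. The average may be unaffected, but the spread grows. The test counts that spread as noise although the day is known for every observation.

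Acuity testing, lens insertion and removal, and the 0-100 ratings are all repeated on each day (Sections 8.3.1 and 8.3.2), so some drift is plausible, though its size is unknown. At stake are power and interval width for HCVA, the primary endpoint, and likewise for any ratings analysed as continuous. The sponsor wants to move wearers of one lens to either of the other two (Section 1). A test that rejects too rarely leans towards a finding of no difference, which would favour that switch.

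**Working it through.** **Inputs from the documents.** 33 subjects for 80% power to detect half a line, and alpha 0.05 with an unnamed multiplicity adjustment (Section 10.1); target of 40 completers (Synopsis).

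**Assumptions.** One line is 0.10 logMAR, so half a line is 0.05. Alpha is two-sided. The trend is linear, at τ logMAR per day. The six possible lens orders are used equally unless stated otherwise.

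**1. The plan's own figure.** No SD is stated, so n = 33 cannot be reproduced directly. Solving backwards:
- Normal approximation: SD = 0.05 × √33 / (1.960 + 0.842) = 0.1025.
- Exact paired t-test (noncentral t, 32 df, noncentrality 0.05 × √33 / SD): SD = 0.0994.

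The second value is used below. With it, power at n = 40 and no trend is 87.3%.

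**2. Effect of a trend under balanced orders.** Over the six orders, the day of lens A minus the day of lens B takes the values −1, −2, 1, −1, 2, 1. The mean is 0, so there is no bias. The mean square is 12/6 = 2, so the variance of the paired difference rises by 2τ²:

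SD(τ) = √(0.0994² + 2τ²)

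| τ per day | SD | Variance ratio | Power, n = 40 | n for 80% |
|---|---|---|---|---|
| 0 | 0.0994 | 1.00 | 87.3% | 33 |
| 0.01 | 0.1004 | 1.02 | 86.7% | 34 |
| 0.02 | 0.1034 | 1.08 | 84.7% | 36 |
| 0.03 | 0.1081 | 1.18 | 81.4% | 39 |
| 0.05 | 0.1220 | 1.51 | 71.5% | 49 |

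At n = 40, power falls to 80% at τ of about 0.033.

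**3. With period adjusted.** Simulation (4,000 trials per setting, n = 40) regressed each paired difference on its day indicators. Power was 87–88% with near-balanced orders, and 85–86% when each subject's order was drawn independently, with no dependence on τ. Type I error stayed near 5%.

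**4. Calibration of the unadjusted test.** With near-balanced orders, its simulated type I error was about 3.4% at τ = 0.03 and 1.8% at τ = 0.05. With independently drawn orders it stayed near 5%.

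**5. When bias would arise.**
- Forty subjects over six orders gives 6 per order and 4 left over. In the worst case the four leftover differences sum to 2 + 1 + 1 − 1 = 3, a shift of 3/40 = 0.075τ, or about 0.002 logMAR at τ = 0.03.
- With independently drawn orders the expected shift is 0; its root mean square is τ√(2/40) = 0.22τ.
- A systematic 2:1 imbalance in which of two lenses comes first would give (2/9)(−4) + (1/9)(4) = −0.44τ. That is 0.009 logMAR at τ = 0.02 and 0.022 at τ = 0.05, with type I error of about 7.5% and 21%. Nothing in the documents points to such an imbalance.

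**6. Pooling the error variance.** Two lenses are omafilcon A and one is somofilcon A (Table 1), so the three differences need not have equal SDs. Assume 0.07 for the same-material pair and 0.115 for the other two. One pooled error variance then gives a type I error of about 8.4% for a cross-material pair and 0.6% for the same-material pair. A pair-specific, period-adjusted contrast gives about 5–5.5%.

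**The case against.** The plan does name analysis of variance, the usual tool for three lenses in one subject, and that could carry a period factor. This stands in part: no factors are listed, so period is neither planned nor excluded, and the change amounts to stating them.

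The size of the loss rests on an assumed trend and an inferred SD. This stands. The largest trend shown, 0.05 per day, means 0.10 logMAR from the first day to the third: a full line, in adapted lens wearers with spectacle acuity of 20/25 or better (Section 8.1). At 0.01–0.02 per day the loss is about 1–3 points.

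The paired t-test also has a real merit, in that each comparison uses its own variance. A simple random-intercept model with period would give that up, as step 6 shows. This stands and shapes the fix.

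Stronger readings are tempting but unsupported:
- **Lens estimates are biased.** Order is randomised, the table is unseen, and 40 not being a multiple of 6 matters negligibly. Exclusion of missing points could make the realised orders less even, but no figure suggests by how much.
- **False positives are inflated.** With balanced orders the test errs the other way.
- **The omission leaves the study short of power.** At unadjusted alpha, power stays above 80% up to about 0.033 per day. At 0.05/3 (one possible adjustment; the method is not named) the same formula gives 75% even with no trend, so that shortfall is not caused by period.
- **A practice effect is certain because one chart is reused.** The supplied text does not describe the chart versions.

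**Conclusion.** The point holds as one of efficiency and calibration. Section 10.1 plans no adjustment for day in a three-day randomised comparison. Any trend would widen the intervals and, with balanced orders, make the test conservative. For HCVA, under the assumptions listed, the cost is between under 1 point of power (0.01 logMAR per day) and about 16 points (0.05 per day); only the lower part of that range is modest. The ratings could drift more than acuity does, but the documents give no figures from which to size that. Bias is a possibility that depends on the realised orders, not a finding. This is a cheap improvement.

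**What to change.** In Section 10.1, for HCVA and for 0-100 ratings treated as continuous, estimate each pairwise lens difference with adjustment for period. Either of two methods will do:

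- A repeated-measures mixed model with lens and period as fixed effects, an unstructured within-subject covariance by lens, and a small-sample degrees-of-freedom correction such as Kenward–Roger. Do not use a single pooled error variance.
- A regression of each paired difference on period. Each day indicator is +1 if the first lens was worn that day, −1 if the second was, and 0 otherwise; the first day is the reference. The intercept is the lens difference.

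Report 95% confidence intervals, apply the multiplicity adjustment already promised and name its method, and keep the paired t-test as a sensitivity analysis. State how the lens orders are balanced. The mixed model also keeps a subject who misses one lens and would otherwise drop out of two of the three paired tests; this is a minor gain.

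The cost is wording, a few lines of code, two degrees of freedom for period and a few covariance parameters. It needs no new data, since the day of wear is already known. If there is no trend, the power lost is about 0–1 point with near-balanced orders. With independently drawn orders the pair-by-pair regression loses about 1.6 points (87.2% to 85.6% in simulation), which is a further reason to balance the orders.
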